5.5 Discontinuation of patient, study or site participation

Treatment discontinuation: Patients have the right to withdraw from the study at any time and for any reason, without being required to state their reasons for doing so. The investigator has the right to discontinue a patient from study treatment or from the study for any medical condition that the investigator determines may jeopardize the patient's safety if he or she continues in the study, for reasons of non-compliance (e.g., missed doses, visits), if the patient becomes pregnant, or if the investigator determines it is in the best interest of the patient.

Patients should be withdrawn from the study treatment if they experience disease progression as defined by RECIST v1.1 criteria. An exception to this are patients who develop isolated brain progression as described in section 3.4, and who, in the investigator's judgment, will clinically benefit from the drug.

Further details regarding study discontinuation due to side effects are described in section 7.

Protocol No.: MedOPP112 Protocol date: May 21, 2018

Version 3

Patients who withdraw from study treatment prematurely will be followed up in accordance with section 5.3 except for those patients who withdraw their consent and who do not wish to undergo a follow-up. The main reason for discontinuation should be recorded in the appropriate section of the case report form (CRF).

Study discontinuation: Section 3.7 defines EoS and study discontinuation.

Patients will be withdrawn from the study (e.g., from any subsequent study procedure) for any of the following reasons:

- · Withdrawal of consent.
- Lost to follow up.

If patient is lost to follow-up, site personnel must do their utmost to re-establish contact with the patient and determine the reason for their withdrawal. All measures taken to undertake follow-up should be recorded.

When a patient withdraws before the end of the study, the reason for withdrawal should be recorded in the CRF and in the original document. Patients who withdraw from the study will not be replaced.

In addition, the sponsor reserves the right to terminate this study at any time. Reasons for terminating the study may include, but are not limited to, the following:

- The incidence or severity of AEs in this or other studies indicates a potential health risk to patients.
- Patient enrollment is unsatisfactory.
- Decision of the Scientific Committee once results of interim analysis are known.
- Data recording is inaccurate or incomplete.

6 INFORMATION ON STUDY DRUG

6.1 Study treatment

Once enrolled in the study, the patient will receive study treatment.

The treatment dose will be one tablet of osimertinib (AZD9291) 80 mg for daily oral administration.

Tablets will be packed in child-resistant high-density polyethylene (HDPE) bottles. The bottles dispensed to patients will be specially prepared for the study.

6.2 Drug supplies

The latest version of study document Summary of Product Characteristics for osimertinib (AZD9291) includes updated information on this drug.

The drug will be supplied by AstraZeneca to the sponsor, who will be responsible for its distribution to participating hospitals until the end of study, which will be after 78 weeks of follow-up of the last patient enrolled. From this point onwards, patients may continue to receive the commercial drug, if your doctor considers it appropriate.

EudraCT No.: 2015-004828-66 Protocol No.: MedOPP112 Protocol date: May 21, 2018

Version 3

The sponsor will supply sites with HDPE (high-density polyethylene) bottles containing osimertinib (AZD9291) 80 mg tablets for oral administration and HDPE (high-density polyethylene) bottles containing osimertinib (AZD9291) 40 mg tablets for oral administration. The smaller dose tablets can be taken in cases that call for a reduction of the dose of osimertinib (AZD9291) under circumstances described in Section 6.9.

6.3 Formulation and packaging

The sponsor will supply drug formulation for oral administration to sites in HDPE (high-density polyethylene) bottles containing 80 mg or 40 mg tablets. Tablets will be packed in bottles with child-resistant closures. The bottles will be dispensed to patients in packages specially prepared for use in this study.

Labels will be prepared in accordance with Good Manufacturing Practice and local regulatory guidelines. The label text will be translated into the local language. The label will include the name of the sponsor, study code, text stating that the drug is for clinical trial use only and/or any other market-specific requirements. All study drugs should be kept in a secure place under appropriate storage conditions. The investigational product label on the pack will specify the appropriate storage.

6.4 Dispensation

The unique patient number (UPN) will be recorded on the label affixed to the box in the areas set aside for this information when drug is assigned to the patient. Site personnel should ensure that the patients fully understand the instructions given to them regarding self-administration. Patients should be given an adequate supply of the drug that will last until the following study visit. Any unused and/or empty bottles should be returned to the site during the next study visit. Unused medication that has been returned SHOULD NOT be supplied to patient.

Two doses of osimertinib (AZD9291), 40 mg and 80 mg tablets for oral administration, will be supplied. At each visit, sufficient osimertinib (AZD9291) for the following programmed cycles (21 days per cycle) to last until the next visit, + 4 additional days per cycle (overage) will be distributed. Individual bottles will be dispensed in accordance with the medication identification numbers provided by the sponsor. Subjects should swallow one osimertinib (AZD9291) 80 mg tablet once daily, commencing on Day 1 of each cycle.

At each dispensing visit, the patient will only receive tablets of one strength or the other, not both. In the event a dose change is required, the patient will be asked to return all previously supplied medication and new tablets will be supplied to them.

6.5 Administration

Patients will be treated with osimertinib (AZD9291) administered orally, once a day. The initial dose of osimertinib (AZD9291) is of 80 mg per day. Treatment with osimertinib (AZD9291) is continuous. Each 21-day treatment period represents one cycle, and treatment will begin on day 1 of the first cycle. Routine pre-medication is not recommended for osimertinib (AZD9291). In the event of relevant toxicity, dose reduction is recommended to improve tolerance.

At each visit, sufficient osimertinib (AZD9291) for the following programmed cycles (21 days per

Protocol date: May 21, 2018 Version 3

cycle) to last until the next visit, + 4 additional days per cycle (overage) will be distributed. Individual bottles will be dispensed in accordance with the medication identification numbers provided by the sponsor. Subjects should swallow one osimertinib (AZD9291) 80 mg tablet once daily, commencing on Cycle 1 Day 1.

Tablets will be taken once daily and may be taken with or without food. The tablet should be swallowed whole with water and should be crushed, split or chewed.

If the patient cannot swallow the tablet, it may be diluted in 50 mL of non-carbonated water and immediately swallowed. Subsequently, the patient should refill the glass with water and swallow it again in order to take the full dose. No other liquid may be added for this purpose.

In case of administration via nasogastric feeding tube, the same process described above should be carried out using volumes of 15 mL for the initial dilution and 15 mL to clean the potential medication waste. The remaining 30 mL should be administered via nasogastric feeding tube appropriately according to the manufacturer's instructions. This alternative administration should be carried out until a maximum of 30 minutes upon dilution.

The initial dose of 80 mg AZD9291 can be reduced to 40 mg AZD9291 once daily, under circumstances described in Section 6.9. Doses should be taken approximately 24 hours apart at the same time point each day. If a subject misses a scheduled dose, it is acceptable to take the dose within a window of 12 hours. If it is more than 12 hours after the dose time, the missed dose should not be taken, and subjects should be instructed to take the next dose at the next scheduled time. If a subject vomits after taking their osimertinib (AZD9291), they should not make up for this dose, but should take the next scheduled dose. Any change from dosing schedule, dose interruptions, and dose reductions should be recorded in the CRF.

Drug treatment is to begin within 2-4 weeks of reception of the tumor sample at the central reference laboratory. Patients will continue receiving the assigned therapy until objective disease progression, symptomatic deterioration, occurrence of an unacceptable side effect, death, withdrawal of consent or the end of the trial (78 weeks from the first dose of the last enrolled patient), whichever occurs first.

However, patients may continue to receive treatment with commercial osimertinib (TAGRISSO) according to the investigator's judgment. In this case, the investigator should follow-up on the patient in an appropriate manner, according to standard clinical practice.

6.6 Medication errors and overdose

Medication errors in this study may arise when the drug is administered at the wrong time or when the wrong dose strength is taken. Patient medication errors should be recorded in the relevant section in the CRF. In the event of an error in the administration of the medication, the sponsor should be informed immediately.

Protocol date: May 21, 2018 Version 3

Medication errors must be reported irrespective of the presence of an associated AE/SAE, including:

- Medication errors involving patient exposure to the investigational medicinal product;
- Any possible medication errors or use of the medication not defined in the protocol which implicate the participating patient or not.

Regardless of whether the medication error is accompanied by an AE or not, in the judgment of the investigator, the medication error should be recorded in the adverse event (AE) page.

6.7 Treatment compliance

At the beginning of each cycle, patients will be required to return all bottles of osimertinib (AZD9291) for drug count. The members of the study staff are responsible for counting osimertinib (AZD9291).

Drug accountability will be performed on Day 1 of every cycle prior to dispensing drug for the next cycle. The number of remaining tablets will be documented and recorded.

To be considered compliant, each study patient must have received at least 80 % of the planned number of doses of primary treatment based on the number of days of actual dose administration. If a dose titration is required, see instructions provided in section 6.9.

6.8 Drug storage and accountability

Investigators and site personnel are reminded to continuously observe storage temperatures and to verify the correct operation of thermometers, as required for the correct storage of the investigational product. This includes thermometers for room temperature storage and thermometers for fridge storage.

At the end of the study, the sponsor will give instructions regarding the disposal of unused investigational products. If the sponsor authorizes the destruction of medication at the study site, the investigator should ensure that the materials are destroyed in accordance with the relevant environmental regulations, institutional policy and any special instructions given by the sponsor. The destruction of these materials will be recorded in an appropriate manner.

6.9 Dose change

Every effort should be made to administer study treatment based on the planned dose and regimen. Nevertheless, in the event of a significant treatment-related side effect, an adjustment can be made in the administration of the study drug as described in the following sections.

In case of toxicity, symptomatic treatment and dose changes should be made according to the following instructions. Repeated dose interruptions are allowed as required, for a maximum of 3 weeks each time (a delay of up to 3 weeks after the planned drug administration is allowed). As long as the study drug administration can be continued, the patient will remain on trial treatment. In case of doubt, please contact the medical monitor immediately.

Protocol No.: MedOPP112 Protocol date: May 21, 2018

Version 3

6.9.1 Dose reduction

In the event of a significant treatment-related side effect, the osimertinib (AZD9291) dose can be interrupted, delayed and/or reduced, as described below. In the event of multiple side effects, dose change should be based on the worst toxicity observed. Patients are instructed to notify the investigator the moment he/she notices any adverse signs or symptoms.

After an interruption in administration or a delay in a cycle, a dose reduction may be necessary when treatment is to be resumed. No specific dose adjustments are recommended for Grade 1 or 2 treatment-related toxicity.

However, investigators should always use their judgment when treating patients, in accordance with the specific clinical circumstances. A reduction in osimertinib (AZD9291) dose by 1 dose level (Table 2) is permitted, based on the type and severity of the side effect. Patients requiring more than 1 dose reductions will be discontinued from the study and entered into the follow-up phase. All dose changes/adjustments should be clearly noted in the original patient record and in the CRF.

Table 2. Osimertinib (AZD9291) dose reduction

Dosing level	Osimertinib (AZD9291) for 3 weeks
Starting dose	80 mg/day
- 1	40 mg/day
	Discontinue study treatment

Table 3. Osimertinib (AZD9291) dose adjustment after adverse reactions

Organ involved	Adverse Reaction	Dose change
Lung	ILD/Pneumonia	Discontinue the treatment . permanently.
Heart	QTc interval >500 ms at least in 2 different ECGs.	Maintain of osimertinib (AZD9291) until the QTc interval <481 ms or go back to baseline results if they are ≤481 ms and then, restart at a reduced dose (40 mg).
	QTc interval prolongation with signs/symptoms of severe arrhythmia.	Discontinue osimertinib (AZD9291) permanently.
Other	Grade 3 or higher adverse reaction.	Discontinue osimertinib (AZD9291) up to 3 weeks.

EudraCT No.: 2015-004828-66 Protocol No.: MedOPP112 Protocol date: May 21, 2018

Version 3

If the grade 3 adverse reaction improves to grade 2 or lower after osimertinib discontinuation up to 3 weeks	The administration of osimertinib (AZD9291) may start at a normal dose (80 mg) or at a reduced dose (40 mg).
If the grade 3 adverse reaction improves to grade 2 or lower after osimertinib discontinuation up to 3 weeks.	Discontinue osimertinib (AZD9291) permanently.

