6.9.2 Interruption of administration

The dose may be interrupted, when necessary, until the resolution of toxicity. Depending on when the adverse event is resolved, an interruption in therapy may cause the patient to miss subsequent doses that have been scheduled for that cycle and even delay the start of the next cycle.

Administration of osimertinib (AZD9291) should be permanently discontinued under the following circumstances:

- Interstitial pneumonitis.
- Hepatic insufficiency.
- Gastrointestinal perforation.
- Corrected QT interval prolongation with signs/symptoms of severe arrhythmia.
- Suspension of treatment lasting more than 3 weeks.

If the adverse event that gave rise to the interruption of treatment is resolved within that same cycle, the treatment can be resumed in that cycle. Doses not administered due to toxicity will not be replaced in that same cycle. The need for a dose reduction when treatment is to be resumed should be assessed in keeping with the criteria defined above, unless otherwise agreed upon by the investigator and sponsor. If a dose reduction is made within the cycle, the patient should come to the site to receive a new supply of the drug. If the treatment is interrupted for reasons other than treatment-related toxicity (e.g., surgery not related to cancer) for a period >2 weeks, treatment can only be resumed after consultation with the sponsor.

The appropriate follow-up assessments should be performed until adequate resolution has been reached, in the judgment of the investigator. If these parameters are not met within 3 weeks after the dose interruption (including the scheduled treatment week during which the patient did not receive treatment), then the treatment should be considered permanently discontinued. Treatment can be resumed in cases where patients have recovered from a treatment-related side effect after a period in which treatment has been discontinued for more than 3 weeks or after the cycle has been delayed, but only if treatment offers a clinical benefit to the patient in the judgment of the investigator. In these cases, it is left to the discretion of the investigator after consultation with the sponsor.

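### Protocol Table 3 (Heart) says to maintain osimertinib at QTc above 500 ms and then restart it at 40 mg; the cell contradicts itself, and a hold is evidently meant

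*Protocol*

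**What the plan says.** Protocol 6.9 makes the dose tables operative: in case of toxicity, "dose changes should be made according to the following instructions". Table 3 in section 6.9.1 has two Heart rows.

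- The first is triggered by a QTc above 500 ms on two or more different ECGs. Its action begins "Maintain of osimertinib (AZD9291) until the QTc interval <481 ms or go back to baseline results". It attaches a condition that the baseline value be no higher than 481 ms, and ends "and then, restart at a reduced dose (40 mg" mg), the bracket closing there.
- The second covers QTc prolongation accompanied by features of severe arrhythmia and requires a permanent stop. Section 6.9.2 repeats it in its list of permanent discontinuations: "Corrected QT interval prolongation with signs/symptoms of severe arrhythmia".

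The general rules around the table are permissive. Section 6.9.1 says that after a significant treatment-related side effect the "dose can be interrupted, delayed and/or reduced, as described below". Section 6.9.2 says "The dose may be interrupted, when necessary, until the resolution of toxicity". The SAP repeats the QTc eligibility limit but gives no action for a QTc above 500 ms on treatment.

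**The concern.** The verb at the start of the cell and the verb at its end cannot both be right. Taken at face value, the first keeps the patient on the current dose (80 mg/day at the starting level) until QTc has come down. The only protective step, the reduction to 40 mg, would then follow recovery. That is the unsafe direction for an error in a safety table.

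What is at stake is the handling of an individual patient with marked QTc prolongation and no arrhythmia signs. Nothing in the estimation or testing of the response rate depends on it.

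**Working it through.** No formula applies, and the plan gives no figure to reproduce. The check has three steps.

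**1. Which readings of the cell are coherent?**

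- *Literal (keep dosing).* Dosing continues until QTc is below 481 ms and the drug is then restarted. Nothing was stopped, so there is nothing to restart. Incoherent.
- *Withhold.* Stop, wait for QTc below 481 ms or a return to a qualifying baseline, and restart at 40 mg. Coherent. It agrees with Table 2, where level -1 is 40 mg/day, and with the interruption rule in 6.9.2.
- *A lost noun* (for example, maintain the interruption of osimertinib). Coherent, with the same meaning as *withhold*.

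Both coherent readings are a hold. The rows around it agree: Lung, severe arrhythmia and reactions of grade 3 or higher all begin with stopping the drug, the last for up to 3 weeks. Only this row opens with the opposite verb.

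**2. Does any other provision require the hold?**

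| Provision | What it does | Requires a hold at QTc above 500 ms without arrhythmia features? |
|---|---|---|
| Protocol 6.9.1, text before Table 2 | Permits interruption, delay or reduction; tells investigators to use judgment | No, permissive |
| Protocol 6.9 | Allows repeated interruptions of up to 3 weeks each | No, permissive |
| Protocol 6.9.2, opening | Permits interruption until toxicity resolves | No, permissive |
| Protocol 6.9.2 list and second Heart row | Permanent stop | No, needs severe arrhythmia features |
| Table 3, Other row | Stop for up to 3 weeks at grade 3 or higher | No, QTc has its own Heart row |
| Protocol 3.2 and 3.5 | Treatment ends for an adverse event that the investigator thinks could do serious or lasting harm | No, rests on judgment and ends treatment |
| Protocol 5.2, toxicity paragraph | New bottles depend on clinical evaluation and local laboratory results | No, does not name the ECG or reach tablets already supplied |
| SAP | No on-treatment QTc action | No |

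The Heart row is therefore the only specific instruction for this event, and nothing elsewhere overrides its verb.

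**3. Can a size be put on it?** No. The documents do not say how many patients reached this threshold, how long QTc took to recover, or whether anyone is still on study drug. The gap between the 500 and 481 ms thresholds, the halving from 80 to 40 mg and the 78-week treatment limits describe the rule and the calendar. None of them measures exposure or harm.

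**The case against.** The strongest reply is that no site could follow the literal reading. The cell sits under dose changes, ends in a restart at a lower dose, and is followed by a permanent stop for the worse QTc event, so a clinician would see that a hold is meant. Several provisions support that clinician: judgment under 6.9.1, discontinuation for potentially serious harm under 3.2 and 3.5, interruptions allowed under 6.9 and 6.9.2, and the instruction "In case of doubt, please contact the medical monitor immediately". Section 6.9.2 also says "The appropriate follow-up assessments should be performed until adequate resolution has been reached, in the judgment of the investigator". This stands as a reason to rate the likelihood of harm low. It does not make the rule correct, because a dosing table should not depend on readers overriding its verb.

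The second reply is that the fault may not be in the source. The opening words are ungrammatical, and the Lung row of the same table has a stray full stop, so the page itself may already order an interruption. This also stands. It limits confidence to moderate and puts the source-page check first.

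The third is that SAP section 9 records accrual as closed, so a correction may be moot. That stands only in part. SAP 6.6 has the interim patients continue on treatment, and no passage shows that all of them have stopped.

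**Conclusion.** The point holds as a patient-safety wording correction. Table 3 (Heart) is self-contradictory for QTc above 500 ms on two or more ECGs, a hold is evidently meant, and no other provision requires one in the absence of severe arrhythmia features. It should be fixed, because the row is operative and errs in the unsafe direction. Confidence is moderate and the likelihood of harm is low. The conclusion assumes that the source page reads as the text does here. *Withhold* is an inference from the cell's own ending and the surrounding rules.

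Three stronger readings are tempting, and the documents support none of them.

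- A reader might infer that the protocol means patients to be dosed through marked QTc prolongation. The restart clause and the adjacent rows show otherwise.
- A reader might infer that patients were so dosed, or harmed. The documents contain no data on this.
- A reader might infer an effect on the trial's results. The primary endpoint, sample size, analysis sets and analyses do not depend on this cell.

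**What to change.** Check the source page of Table 3. If it already orders a hold or interruption, the protocol needs no change. If it reads as here, replace *Maintain of* with *Withhold* and leave every other word of the cell alone.

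In particular, keep the term QTc. The trigger in the same row uses it, and eligibility relies on the ECG machine's QTc, so writing QTcF into the release criterion alone could put trigger and release on different corrections. Keep also the condition that the baseline be no higher than 481 ms, since removing a condition from a safety table would be a substantive change.

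Notify any site that still has a patient on study drug. The cost is the page check, a one-verb protocol correction and that notice. No extra ECGs are needed, and nothing changes in the endpoint, sample size or analyses.

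### Three dosing instructions in the protocol (two rows of Table 3 and one sentence in 6.5) are wrong or self-contradictory as written; the intent can be inferred, and the wording should be corrected

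*Protocol*

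**What the plan says.** **Grade 3 reactions (Protocol 6.9.1, Table 3).** A reaction of grade 3 or higher first leads to a hold of up to 3 weeks. Two follow-on rows then open with the same condition, "If the grade 3 adverse reaction improves to grade 2 or lower after osimertinib discontinuation up to 3 weeks". The action in the first is "The administration of osimertinib (AZD9291) may start at a normal dose (80 mg) or at a reduced dose (40 mg"; in the second it is "Discontinue osimertinib (AZD9291) permanently".

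**QTc above 500 ms on at least two ECGs (same table).** The row begins "Maintain of osimertinib (AZD9291) until the QTc interval <481 ms", adds an alternative based on the baseline value, and ends "and then, restart at a reduced dose (40 mg". A separate row covers QTc prolongation with signs or symptoms of severe arrhythmia and orders permanent discontinuation.

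**Tablet handling (Protocol 6.5).** One sentence says to swallow the tablet whole with water and also says that it should be crushed, split or chewed. The next paragraph describes dispersing the tablet in water for patients who cannot swallow it.

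**General rules.** Section 6.9.1 says that, for a significant treatment-related side effect, the "dose can be interrupted, delayed and/or reduced, as described below". Section 6.9.2 says "The dose may be interrupted, when necessary, until the resolution of toxicity". Section 6.9 sends any doubt to the medical monitor.

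**The concern.** These are operative instructions that sites follow when a patient has toxicity or is handed tablets. Each one, taken literally, gives the wrong action or none:

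- A reader who applies the second grade 3 row would end treatment in a patient whom the row above allows to restart.
- A reader of the QTc row sees a verb that suggests continuing the drug, at a QTc level where the rest of the row implies stopping it.
- A reader of 6.5 is told to do something that cannot be combined with swallowing the tablet whole.

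The QTc row carries most of the safety weight, because an error there would mean continued dosing. The grade 3 duplicate errs towards stopping the drug, and the 6.5 sentence cannot be followed as printed, so both weigh less.

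**Working it through.** The plan states no figure for this point, so the check is a comparison of texts.

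**1. Grade 3 rows against 6.9.2.**

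| Situation | Table 3 (6.9.1) | Prose in 6.9.2 |
|---|---|---|
| Recovers within the hold | Row one: restart at 80 or 40 mg. Row two: stop permanently | If resolved within the cycle, treatment can be resumed |
| Does not recover within 3 weeks | No row | Treatment counts as permanently discontinued |
| Recovers after more than 3 weeks | No row | Resumption possible if the patient benefits, at the investigator's discretion after consulting the sponsor |

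The two conditions in the table differ only in a final full stop. The prose needs one row for recovery and one for non-recovery, so the second row has most likely lost a negation. The protocol as a whole therefore does cover non-recovery; the table contradicts that rule for patients who recover. One difference remains: 6.9.2 leaves adequate resolution to the investigator's judgment and does not repeat the table's grade 2 threshold. The table is thus the only place where that threshold is set.

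**2. QTc row.** The opening phrase is ungrammatical, so a word is wrong or missing. A drug can be restarted only after it has been stopped, and 6.9.1 introduces its dose rules as ways to interrupt, delay or reduce the dose. A hold is the only coherent reading. The other places that could supply the instruction do not:

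- The list in 6.9.2 of reasons for permanent discontinuation names only "Corrected QT interval prolongation with signs/symptoms of severe arrhythmia".
- Section 6.10 asks for close ECG monitoring of patients on QT-prolonging drugs and gives no dose action.
- The general rules in 6.9.1 and 6.9.2 permit interruption but give no QTc threshold.

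**3. Tablet sentence.** Swallowing whole and crushing exclude each other. The dispersion procedure for patients who cannot swallow the tablet would hardly be needed if crushing or chewing were routine. The missing word is a negation.

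**4. Who could still be affected.** SAP section 9 records that the interim review took place on 17 December 2018 and that accrual was closed by the funder's decision. The interim required 21 patients assessed to 42 weeks or withdrawn (SAP 6.6). SAP 6.1 (general design) limits study treatment to 78 weeks from the patient's own first dose; Protocol 3.2 counts 78 weeks from the first dose of the last patient enrolled.

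- If enrolment paused for the interim, as the SAP's statement that recruitment resumes afterwards suggests, even the last patient had reached 42 weeks. Both limits then leave at most 78 − 42 = 36 weeks, a range of 0 to 36.
- If enrolment did not pause, a patient who started just before closure could have had up to 78 weeks left.

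The documents do not say which applied, or whether anyone is still on study drug.

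**The case against.** The strongest case on the other side is that these are typing or translation slips that no competent site would misread. Section 6.9.2 gives the grade 3 rule in prose, the word restart settles the QTc row, the 6.5 sentence corrects itself, and the medical monitor is on call for doubt. Much of this stands. It limits the practical harm and makes the matter minor. It does not remove the errors, because the referral to the monitor helps only a site that notices the problem.

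A second objection is that the QTc cell may have lost a word when the PDF was read; table text elsewhere in the protocol is visibly damaged. This cannot be excluded for that row, and the original should be checked. It is an unlikely explanation for the grade 3 rows, which are complete cells with different actions, and for 6.5, which is running prose.

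A third is that other text may settle the matter. Section 5.5 refers to section 7 for discontinuation due to side effects, but section 7 as available is the statistical section. The statement that no other dose action exists for QTc above 500 ms without arrhythmia is therefore limited to the text available.

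A reader might also infer more than the documents support:

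- *That the protocol orders continued dosing at QTc above 500 ms.* It does not; the row makes sense only as a hold.
- *That non-recovery from a grade 3 reaction has no rule.* It has one, in 6.9.2.
- *That patients were misdosed.* The documents give no rate of grade 3 reactions or of QTc above 500 ms, and no sign that a site acted on the wording. Counting scheduled ECGs would not fill that gap, since it measures neither the frequency of the event nor the chance of misreading.
- *That the trial's result is in doubt.* The primary analysis uses all treated patients regardless of adherence (SAP 7.4). SAP Appendix 2 leaves dosing deviations and failure to withdraw a patient to case-by-case judgment, but for the per-protocol set only.

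**Conclusion.** The point holds as a minor, safety-related wording correction. Three instructions are wrong or self-contradictory as written: the second grade 3 row and the QTc row of Table 3, and one sentence in 6.5. The intent of each can be inferred, with 6.9.2 doing that work for the grade 3 row. The QTc row matters most, because its hold is implied and not stated.

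The size of any practical effect cannot be estimated from the documents. The Simon design and the primary analysis are untouched. The conclusion assumes that the printed text matches the original, which needs checking for the QTc cell, and that no unseen section gives a clearer QTc rule.

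**What to change.** Subject to confirmation by the sponsor's medical team, and after checking the QTc cell in the original PDF:

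1. **Table 3, second grade 3 row.** Change the condition to: does not improve to grade 2 or lower within 3 weeks. Keep permanent discontinuation as the action and add: except as 6.9.2 allows.
2. **Table 3, row for QTc above 500 ms.** Open with: Withhold osimertinib until, and leave the restart at 40 mg as it is.
3. **Section 6.5.** Insert the missing negation, so that the tablet should not be crushed, split or chewed.

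The cost is three wording changes in a protocol clarification. Notify sites only if patients remain on study drug. Nothing changes in the design, sample size or analysis.
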